## PROTOCOL SYNOPSIS

Protocol Number	V07
Protocol Title	Control-IQ Observational (CLIO) US Post-Approval Study
Device	t:slim X2 insulin pump with Control-IQ technology (Control-IQ System)
Type of Protocol	Post Approval Study
Rational	
This post-approval study is primarily designed to collect safety data on this US FDA-cleared product. Several secondary endpoints assessing the effectiveness of this product in real-world use will also be collected. The t:slim X2 insulin pump with Control-IQ technology will be used as intended and in accordance with FDA-approved labeling.

Objectives	
Primary objective: To demonstrate, in a real-world setting, the safety of the Control-IQ System for the management of type 1 diabetes by assessing the rate of severe hypoglycemia (SH) and diabetic ketoacidosis (DKA).
 
Secondary objective: To demonstrate, in a real-world setting, the effectiveness of the Control-IQ System for the management of type 1 diabetes by assessing the impact on patients' glycemic outcomes and user experience in the real world, during the first 12 months of use.

Primary Endpoints	
Safety Endpoints:
 
 
1) The incidence rates of severe hypoglycemia (SH) and diabetic ketoacidosis (DKA), and
 
2) The safety of the automatic population of CGM readings into the bolus calculator of the Control-IQ System
 
 
Secondary Endpoints:
 
 
3) To determine glycemic outcomes as a measure of efficacy of the Control-IQ System, and
 
4) To demonstrate patient-reported satisfaction with and trust in the Control-IQ System, usability of the system, and sleep quality.
 

Duration of Study	All enrolled subjects will be monitored for outcome data for 12 months after starting the Control-IQ System.
Study Design	This post-approval study is a single-arm, prospective study. It is designed to assess 12-month safety in a real-world setting, and to support the continued assessment of the Control-IQ System for the treatment of type 1 diabetes in the United States. In addition, data will be collected to assess glycemic outcomes and user experience.

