Inclusion/Exclusion Criteria	
Inclusion Criteria:
 
 
1. Patients with self-reported type 1 diabetes who have been prescribed the Control-IQ system.
 
2. At least 6 years of age
 
3. Using Humalog or Novolog insulin
 
4. For females, not pregnant or planning pregnancy in the next 12 months.
 
5. Agreement to use the t:slim X2 with Control-IQ technology, and to continue use for at least 12 consecutive months after study enrollment.
 
6. Agree to provide HbA1c result, obtained within the 6-month period prior to enrollment.
 
7. Ability to respond to alerts and alarms, and to provide basic diabetes self-management.
 
8. Patients who reside full-time in the United States.
 
9. Willingness to download the t:connect Mobile application to their Smartphone and keep it active throughout the study. Patients unable to use t:connect Mobile application must be willing to manually upload their insulin pump data to t:connect every three months and at the completion of the study.
 

	
10. Subject has read, understood and agreed to participate in the study, and has electronically signed the Informed Consent Form (ICF).
 
Exclusion Criteria:
 
 
1. Self-reported type 2 diabetes
 
2. < 6 years of age
 
3. Use of any glucose-lowering therapy other than Humalog or Novolog insulin
 
4. Inability to respond to alerts and alarms, or to provide basic diabetes self-management.
 
5. Pregnancy
 
6. Subjects who have not signed the ICF.
 

Procedures in Screening/Baseline Period	
Study subjects will be recruited via automated electronic outreach from new users of the Control-IQ System. All customers receiving new pumps and receiving Control-IQ software updates will be initially screened for inclusion/exclusion criteria electronically via filters in the CRM system. Invitations to participate will be sent to all customers who initially qualify for the study. A positive response from a customer will initiate the informed consent process and provide a second screening and baseline survey. An electronic signature of consent will be obtained from customers who qualify after the second screening. Once consent is obtained, a baseline survey will collect PROs (user experience and adverse events) related to therapy prior to starting Control-IQ.

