Periodic Data Collection procedures	
100% of calls to Tandem Customer Technical Support will be screened for reportable AEs based on the definitions of SH and DKA included in this protocol. Outreach surveys will be deployed to all study participants: Monthly to collect AE incidence, and at 3, 6 and 12 months to collect other PROs (See Table 1).

Management of Adverse Events	
Safety information will be collected on an ongoing basis throughout the study as Tandem becomes aware of device-related AEs. These events will be recorded electronically from both inbound reports from customers and assessed through outreach to patients. The event, date of onset, severity, seriousness, duration and relationship to the device will be documented. All reported device-related AEs will be followed until they are adequately resolved or stabilized, until study completion/termination, or until number of outreach attempts made by clinical personnel corresponds with company's Customer Technical Support policy for adverse and device issue event outreach, whichever comes first. Safety events will be summarized based on FDA codes.

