#### **Secondary objectives:**

- 3) To determine glycemic outcomes during real-world use of the Control-IQ System, and
- 4) To demonstrate patient-reported satisfaction with the device, trust in the Control-IQ System, usability of the system, and sleep quality.

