### Data Collection:

The data will be collected per the schedule outlined below:

Procedure/Assessment	Baseline*	Monthly	Months 3 and 6	Final
Informed Consent	X			
**Release of Medical Records				
Screening for eligibility	X			
Report of incoming AEs		X		X
Outreach for AEs	X	X		X
User Experience	X		X	X

Psychosocial Outcomes	X	X	X
-----------------------	---	---	---

\*Includes demographics, frequency of AEs

\*\*Only requested as needed to collect additional information on reported AEs

Investigators will be provided a process for assigning a de-identified number to the subject and will be required to keep any study paperwork or electronic files in a secure private area. Electronic audits will be in place to help ensure that data entered is within reasonable limits.

**Informed Consent Process:** All subjects must electronically sign the ICF (see **APPENDIX B**) approved by the IRB to be enrolled in the study. The subject will receive study team contact information (email and telephone) and be given ample opportunities to ask questions about the procedures, required schedule of data collection, and the benefits and risks of participating in the study before signing the ICF. All subjects will receive an electronic copy of the ICF to keep for their records. Subjects will be informed of any revisions to the ICF and any revisions must be electronically signed and kept in the subject study file. In addition, a signed Release of Medical Records form may be obtained if needed to collect additional information on reported Adverse Events to allow the investigators to obtain accurate event information when necessary. Acquisition of the informed consent, Release of Medical Records form (if applicable) and any revisions will be documented in the survey database.

**Demographics:** The following demographic data will be obtained: date of birth, gender, race, ethnicity, educational level, socioeconomic status, residence, employment status, weight, height, and type of health insurance.

**Medical History:** Medical history, including existing comorbidities deemed clinically relevant (e.g. retinopathy, nephropathy, neuropathy, history of cardiovascular events) will be collected at baseline. In addition, details specific to type 1 diabetes, including age at diagnosis, duration of disease, previous therapy, most recent HbA1c within the past 6 months, frequency of SH and DKA, and family history will be collected from the study subject in the baseline questionnaire.

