Secondary endpoints will be calculated as means/medians as appropriate based on data extracted from the Tandem t:connect web application and patient reported outcomes. Sensor-glucose concentrations will be analyzed per recent international consensus guidelines, to include time in target range 70-180 mg/dL, time  $> 180$  mg/dL, time  $> 250$  mg/dL, time  $< 70$  mg/dL, time  $< 54$  mg/dL.

Outcomes will be analyzed quarterly and tabulated using standard statistical tools such as SPSS, R and Python.

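### Secondary endpoints are summarised only as means or medians, so with 25% planned attrition the visit means cannot show the impact that the synopsis claims

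*Combined protocol and SAP*

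**What the plan says.** The secondary-endpoint paragraph under Primary Outcome reads: "Secondary endpoints will be calculated as means/medians as appropriate based on data extracted from the Tandem t:connect web application", and it adds patient-reported outcomes as the second source. The Statistical Analysis row of the synopsis says the same. Outcomes are to be tabulated quarterly. The document gives no change from baseline, longitudinal model, analysis window, analysis set or missing-data rule for these endpoints.

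The objectives are worded in two ways. The synopsis aims to demonstrate effectiveness by "assessing the impact on patients' glycemic outcomes and user experience in the real world, during the first 12 months of use". The body, under Secondary objectives, is more modest on glycemia: "To determine glycemic outcomes during real-world use of the Control-IQ System". For satisfaction, trust, usability and sleep quality, however, the body still speaks of demonstrating.

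On data collection, the synopsis states that "a baseline survey will collect PROs (user experience and adverse events) related to therapy prior to starting Control-IQ". Follow-up surveys come "at 3, 6 and 12 months to collect other PROs". The only glycemic measure scheduled at baseline is HbA1c ("most recent HbA1c within the past 6 months", under Data Collection). The glycemic endpoints themselves are CGM metrics, and no pre-start CGM period is defined for them.

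The synopsis plans for 2,063 recruited subjects, 25% attrition and 1,547 completers. The section on Subject Withdrawal or Termination keeps data gathered before withdrawal but does not address values missing afterwards.

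**The concern.** Impact implies a contrast: the same people with and without the system, or before and after starting it. A mean at month 12 set beside a mean at baseline is such a contrast only if the same people stand behind both. Here they will not. A quarter of the sample is expected to be lost, and subjects with no Control-IQ data 120 days after the baseline survey become screen failures after giving baseline answers.

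If those who stop answering differ from those who continue, the visit means move even though no individual has changed. A large sample does not help, because it narrows the interval around the shifted value. The baseline PROs, which could separate the two effects, have no stated analytic use. For CGM metrics the difficulty is more basic: without a defined pre-start period, values during use describe control on the system but not its effect.

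**Working it through.** **1. The plan's own figures.** 2,063 × 0.75 = 1,547.25, and 1,547 / 0.75 = 2,063 after rounding up, so the synopsis figures reproduce. Step 3 of the sample-size section instead expects 1,354 completers. That would be 1 − 1,354/2,063 = 34.4% attrition, which does not match the stated 25%.

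**2. Shift of the responder mean.** Let a be the fraction not responding and d the responder mean minus the non-responder mean, in SD units. The mean over everyone is (1 − a) × responder mean + a × non-responder mean, so the responder mean lies above it by a × d. The documents give no value for d; 0.3 to 0.5 SD is an assumed range.

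- a = 0.25: 0.25 × 0.3 = 0.075 SD; 0.25 × 0.5 = 0.125 SD
- a = 0.344: 0.344 × 0.3 = 0.10 SD; 0.344 × 0.5 = 0.17 SD
- d = 0: no shift at either attrition level

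**3. Sampling error for scale.** The 95% half-width of a mean is 1.96/√1,547 = 0.050 SD (0.053 SD at n = 1,354). Over the assumed range the shift is 0.075/0.050 = 1.5 to 0.125/0.050 = 2.5 half-widths at 25% attrition.

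**4. Which analysis removes it.** A simulation of one million subjects used a standardised score, true change zero and 25% dropout, more likely at lower baseline scores. The logistic slope (0.3 to 1.0) and the correlation between baseline and month 12 (0.4 to 0.8) are assumed. The estimated change, which should be zero, was:

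| Analysis | Apparent change (SD) |
|---|---|
| Month-12 responder mean minus baseline mean of all enrolled | +0.03 to +0.17 |
| Paired change in completers only | −0.13 to −0.015 |
| Baseline-adjusted, standardised to all enrolled | 0.00 |

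The paired completer analysis is biased the other way by regression to the mean: those who stay have higher baseline scores. The baseline-adjusted estimate is unbiased here because dropout was made to depend on baseline alone. If it depends on the unseen month-12 score, no such model removes the bias fully, hence the sensitivity analysis below.

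**The case against.** The case for leaving the plan alone has weight. The study is mainly about safety, has one arm, and attaches no hypothesis or success criterion to any secondary endpoint. The body asks only what glycemic outcomes are during use, which descriptive values answer. A literature comparator is planned, and a detailed analysis plan is promised before the first tabulation. This keeps the point minor but does not close it. The comparator values are tabulated only for SH and DKA, and an external mean gives no within-person change. The promised plan is not in the document, and the synopsis still speaks of demonstrating effectiveness.

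A second objection stands and narrows the remedy. Subjects cannot report trust in Control-IQ, or its usability, before starting it, and baseline satisfaction concerns a different therapy. Of the four named PROs, only sleep quality is plainly the same construct before and after. The Appendix D instruments are not reproduced in the available text, so comparability of the others cannot be judged here.

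A reader might infer more than the documents support:

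- *That only on-treatment values are averaged and baseline is discarded, or that only completers are analysed.* The plan does not say which periods are averaged, and it keeps pre-withdrawal data.
- *That attrition is known to be selective, with satisfied users staying.* Nothing in the documents shows this. It is a risk.
- *That the 25% applies equally to CGM data.* It is a planning figure for the primary endpoints, and CGM data arrive by app or upload, not by survey.
- *That a paired analysis is also more precise.* Treating the two means as independent gives √(1/2,063 + 1/1,547) = 0.0336 SD, against a paired standard error of √(2 × 0.5/1,547) = 0.0254 SD at an assumed correlation of 0.5. But the completers are in both means. With dropout unrelated to scores, the variance of the difference is 1/1,547 + 1/2,063 − 2 × 0.5/2,063 = 1/1,547, so the standard error is 0.0254 SD either way. The argument is about bias, not precision.

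**Conclusion.** The point holds in limited form and is of low severity. Means and medians by visit do not support a statement about impact when a quarter of subjects are expected to be lost and no missing-data method is given. Under the assumed gap of 0.3 to 0.5 SD and the planned 25% attrition, the month-12 responder mean is off by 0.075 to 0.125 SD, more than its 95% half-width of about 0.05 SD. With no gap there is no bias. The documents give neither the gap nor a threshold for an important PRO difference, so the result shows that bias can exceed random error, not that it will. For CGM metrics the conclusion needs no assumption about attrition: where no pre-start data exist, values during use are descriptive.

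**What to change.** In the analysis plan, before the first tabulation:

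- For PROs that measure the same construct before and after the start (sleep quality, and others only where the Appendix D instrument is comparable), estimate change from baseline at months 3, 6 and 12 with 95% confidence intervals. Use a repeated-measures model on all available visits that includes the baseline of all enrolled initiators, not a paired change in completers.
- Compare baseline scores of responders and non-responders at each visit, and add a missing-not-at-random sensitivity analysis.
- Report trust in and usability of Control-IQ as descriptive follow-up values. Do the same for CGM metrics, except in subjects with pre-start data in t:connect, for whom a pre-start window should be defined.
- Align the synopsis objective with the body's wording on determining glycemic outcomes, so that impact and demonstrated effectiveness are not claimed for endpoints reported descriptively.
- Reconcile the two completer figures (1,547 and 1,354), since the attrition fraction sets the size of any shift.

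No new data are needed. The cost is some added analysis work and a more modest effectiveness claim.

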## **Data Management**

Data from the study will be collected via study databases. Data will be sent in a secured validated format to Tandem Diabetes Care, Inc. on an ongoing basis.

Trained study personnel will be responsible for entering data on the adverse events, as specified in the protocol, applicable device issues and any unscheduled contacts with participants into the eCRF system and according to the eCRF instructions. All other data such as eligibility, medical history and other assessments will be captured directly by participants as part of their responses to the surveys and collected directly as part of the survey database. The eCRF instructions will also provide data entry instructions. Risk-based monitoring of data will be conducted. Data entered in the eCRF will be immediately saved to a central database and changes tracked to provide an audit trail. When data have been entered, reviewed, edited and source data verification (SDV) performed as specified per the clinical monitoring plan, the investigator will be notified to sign the eCRF electronically as per the agreed upon project process, and data will be locked to prevent further editing. A copy of the eCRF will be archived at Tandem Diabetes Care, Inc.

Data verification and data validation checks will be performed by Tandem Diabetes Care, Inc., or its designee(s), using electronic checks comprised of validated computer programs and manual data review. Any data discrepancies will be referred back to the investigator for resolution. After the database has been declared clean it will be locked, and editing in the database will only be allowed with the proper documentation. After database lock, data will be extracted for analysis.

## **LEGAL/ETHICS AND ADMINISTRATIVE PROCEDURES**

### **Good Clinical Practice/Regulatory Compliance**

The procedures described in this study protocol pertaining to the conduct, evaluation, and documentation of this study, are designed to ensure that the sponsor and investigators abide with FDA regulations in accordance with 21 CFR, Parts 50, 56, and 812; applicable state and local regulations; and the standard operating procedures (SOPs) of Tandem Diabetes Care, Inc., and its designee(s).

Independent Institutional Review Boards (IRBs) will provide oversight per local requirements and review documents associated with the study to determine that they comply with all federal, state, and local laws and that the risks to subjects are minimized and reasonable in relation to anticipated benefits per the US Code of Federal Regulations (CFR), Title 21, Part 56, Section 56.111(a).

It is the investigators' responsibility to ensure that adequate time and appropriate resources are available in order to conduct the study. The investigators should also be

able to estimate or demonstrate the potential for recruiting the required number of suitable subjects within the agreed upon recruitment period. The investigators will maintain a list of appropriately qualified personnel to whom the investigators have delegated significant study-related tasks.

### **Investigator Qualification / CV**

The investigators will provide the sponsor with a current curriculum vita and any revisions/updates during the study, as well as those of any staff personnel with significant study responsibilities.

### **Statement of Investigator**

The investigators are required to sign and date a Statement of Investigator form for the original and each subsequent amendment of the protocol, prior to enrolling any subjects under that protocol version.

### **Financial Disclosure**

Financial disclosure statements will be completed for the investigators to disclose potential conflicts of interest (per 21 CFR Part 54). Financial disclosure information will be kept updated as necessary throughout the duration of the study.

### **Investigator Training**

Investigators and their designees will be trained in the informed consent, screening and enrollment procedures, as well as proper documentation of all procedures. Investigators must provide recent certification of GCP training.

### **Responsibilities**

#### **Sponsor Responsibilities**

The sponsor of this study is Tandem Diabetes Care, Inc. of San Diego, CA, US. The sponsor is committed to:

- Protecting the rights, health, safety and welfare of study subjects by the review of IRB approvals and verification of the subject informed consent process.
- Verification of data in CRM, used to initially qualify customers for participation in the study.
- Periodically reviewing the data to ensure that the study is being conducted in compliance with the protocol and the investigators' agreement. Providing the investigators with access to the EDC system and study eCRFs.
- Maintaining a system of study documentation.
- Providing training on key elements of the protocol, including subject inclusion/exclusion criteria, EDC system, and all study procedures.
- Reviewing eCRFs to ensure completeness and accuracy of study data. Investigators will be required to resolve discrepancies via the EDC system.

## **Responsibilities of the Principal Investigators**

The investigators will affirm by their signatures on the Investigator Agreement that they will fulfill their responsibilities relative to the study. The investigator responsibilities include:

- Ensuring that all subjects entering the study conform to the subject inclusion criteria and that no exclusion criteria apply.
- Obtaining IRB approval to conduct the study, prior to enrolling any subjects.
- Submitting the ICF to the IRB for approval prior to initiation of the study.
- Obtaining written informed consent from each subject prior to enrollment and verifying that the correct and approved IRB version is used. The electronically signed ICF will be maintained in the subject's record, and a copy of the signed ICF will be part of each subject's case report file retained by the investigator.
- Accurately reporting adverse events in a timely manner by obtaining information from incoming calls to Customer Technical Service, by outreach via surveys, SMS text and phone, and by review of medical records or physician contact if necessary.
- The investigator will review, correct as needed, and sign off on the accuracy and completeness of the data entered in the EDC system. Original laboratory reports, medical records, etc (if applicable), are to be retained by the investigator, and the resulting data shall be entered onto the appropriate eCRFs.

